In the case of PDNV, the use of postoperative opioids is likely a significant contributory factor, as it occurs hours after the anesthetic agents have been metabolized. This is likely why the use of TIVA, which helps prevent PONV, has no effect on the incidence of PDNV. One mechanism of opioid-induced nausea and vomiting is mediated through D₂ receptors in the chemoreceptor trigger zone in the medulla oblongata.¹² This makes anti-dopaminergic agents, such as olanzapine, ideal to target opioid induced nausea and vomiting. The half-life elimination of orally administered olanzapine is 21-54 hours. The time to peak plasma concentration is approximately 6 hours. Therefore orally administered olanzapine, taken with a small sip of water prior to anesthetic induction, demonstrates ideal pharmacokinetics for the prevention of delayed PDNV. Olanzapine's long half-life, low cost, excellent safety profile with short-term use, and targeting of multiple receptors implicated in nausea and vomiting (especially D₂) make it a hopeful prospect for the prevention of PDNV.

3) Setting of the Human Research

This study will be conducted at the Icahn School of Medicine at Mount Sinai. Consent will be obtained at the Mount Sinai OB/GYN Ambulatory Department at [name] Klingenstein Pavilion E level clinic and OB/Gyn Mount Sinai Faculty Practice Associates (FPA) at [name]

Study medications will be administered in the preoperative holding area in the sixth floor of the Annenberg Pavilion at [name]. The intraoperative protocol will take place in the operating room in which the case is scheduled. An investigator will evaluate the patient postoperatively in the Annenberg sixth floor PACU.

4) Resources Available to Conduct the Human Research

	Protocol Title:	Olanzapine for the treatment of Post-Discharge Nausea and Vomiting after Ambulatory Surgery
	Principal Investigator Name/Contact Info:	[name] [contact]
	Primary Contact Name/Contact Info:	[name] [contact] [name] [contact]
	Date Revised:	1/31/2018
	Study Number:	GCO#15-1297; HSM# 15-00501

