Subjects who consent to and are scheduled for ambulatory surgery under general anesthesia will be invited to participate in the study during a routine preoperative visit prior to the day of surgery by a study investigator. The details of the study will be reviewed and written informed consent will be obtained. Additionally, a flyer describing the study will be displayed at the two participating clinic locations to advertise the study to potential participants. The flyer will instruct interested patients to discuss the study with their gynecologist, or to contact the principal investigator directly. If a patient tells their physician that they are willing to participate, a study investigator will describe the study in detail, answer questions, confirm participant understanding, and provide the written informed consent form for review. Patients who have agreed to participate will have a 12-lead electrocardiogram (EKG) obtained in pre-surgical testing. Alternatively, if an EKG is not obtained prior to the day of surgery, it will be performed the same day in the assessment area prior

	Protocol Title:	Olanzapine for the treatment of Post-Discharge Nausea and Vomiting after Ambulatory Surgery
	Principal Investigator Name/Contact Info:	[name] [contact]
	Primary Contact Name/Contact Info:	[name] [contact] [name] [contact]
	Date Revised:	1/31/2018
	Study Number:	GCO#15-1297; HSM# 15-00501

to surgery. Patient's with a QTc > 450 ms using the Fridericia formula will be excluded.

Subjects will be counseled verbally to avoid alcohol, benzodiazepines, and motor vehicle driving for 24 hours following discharge.

The name and date of surgery of the consenting patient will be given to the Investigational Drug Service of the Mount Sinai Pharmacy for randomization and preparation of the medication. On the day of surgery, an investigator will pick up the medication from the pharmacy for the individual subject, and have the subject take the medication with a small sip of water in the preoperative holding area within one hour prior to entering the operating room. In addition, the patient will be provided with a standardized diary to record episodes of vomiting for the first 24 hours after discharge and will be provided with verbal and written instructions for completing the diary (appendix 1). Subjects will be asked for a preferred contact number for the postoperative phone call and permission to leave a voicemail will be requested.

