Upon entering the operating room, after application of standard monitors, midazolam 2 mg will be administered for anxiolysis. If endotracheal intubation is indicated, general anesthesia will be induced using fentanyl 3-5 mcg/kg and propofol 1.5-2.5 mg/kg and muscle relaxation achieved with succinylcholine 1-2 mg/kg or rocuronium 0.6 mg/kg, at the discretion of the attending anesthesiologist. Rocuronium will be administered as needed to maintain muscle relaxation during the case. If a laryngeal mask airway is to be used rather than an endotracheal tube, anesthesia will be induced with propofol 1.5-2.5 mg/kg. Regardless of method of airway management, anesthesia will be maintained with sevoflurane at concentrations deemed appropriate by the anesthesia provider based on intraoperative hemodynamic and respiratory monitoring. Additional doses fentanyl will be administered also as deemed appropriate by the anesthesia provider based on intraoperative hemodynamic and respiratory monitoring. All patients will receive dexamethasone 8 mg immediately following induction, and ondansetron 4 mg and ketorolac 30mg approximately 30 minutes prior to emergence from anesthesia unless there is a specific contraindication. Intubated patients will receive neuromuscular blockade reversal with neostigmine 0.4-0.7 mg/kg prior to tracheal extubation.

	Protocol Title:	Olanzapine for the treatment of Post-Discharge Nausea and Vomiting after Ambulatory Surgery
	Principal Investigator Name/Contact Info:	[name] [contact]
	Primary Contact Name/Contact Info:	[name] [contact] [name] [contact]
	Date Revised:	1/31/2018
	Study Number:	GCO#15-1297; HSM# 15-00501

In the PACU, as needed ondansetron will be ordered as per the department standard orderset, (ondansetron 4 mg intravenous every 4 hours). However, the standard prochlorperazine 10 mg intravenous once will be removed from the orderset to reduce the risk of neuroleptic malignant syndrome or extrapyramidal symptoms when administered in combination with olanzapine. The patients' experience of nausea and/or vomiting will be assessed at 30, 60, and 120 minutes after surgery by trained study personnel. PACU EPIC records will also be audited to record the need for rescue antiemetic medications.

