Prior to discharge from the PACU, subjects will be assessed for signs of orthostatic hypotension (a decrease of 20 mmHg in systolic blood pressure or 10 mmHg in diastolic blood pressure upon standing). Patients who meet the criteria for orthostatic hypotension will be evaluated and treated with intravenous fluid administration. Upon discharge, patients who had symptoms of orthostatic hypotension will be instructed to ambulate with assistance for the first 24 hours after discharge.

Information entered into the subjects' diary will be obtained during a telephone interview on the afternoon or evening of the first day following surgery. At this time investigators will also screen for adverse events.

Relevant preoperative, intraoperative, and postoperative data will be obtained from the anesthesia record, the EPIC electronic medical record, and the telephone interviews and collected on standardized forms by trained study personnel.

Data to be collected:

Age
BMI
ASA status
Smoking status
History of PONV
History of motion sickness
Total intraoperative fentanyl (mcg)
Total intraoperative propofol (mg)
Total intraoperative rocuronium (mg)
Total intraoperative neostigmine (mg)
Total intraoperative Sevoflurane
Duration of surgery
Total fentanyl dose in PACU (mcg)

	Protocol Title:	Olanzapine for the treatment of Post-Discharge Nausea and Vomiting after Ambulatory Surgery
	Principal Investigator Name/Contact Info:	[name] [contact]
	Primary Contact Name/Contact Info:	[name] [contact] [name] [contact]
	Date Revised:	1/31/2018
	Study Number:	GCO#15-1297; HSM# 15-00501

Total oxycodone dose in PACU (mg)
Rescue antiemetics in PACU (yes/no)
Ondansetron total dose (mg)
Length of PACU stay (minutes)
Vomiting in PACU (#episodes at least 1 min apart)
Nausea in PACU (highest number reported on 11 point Likert scale)
Post-discharge vomiting (#episodes at least 1 minute apart)
Post-discharge nausea (highest number reported on 11 point Likert scale)

g) Specimen Banking

N/A

h) Data Management and Confidentiality

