[name] and [name] are board certified anesthesiologists with expertise in the perioperative management of patients. All subjects will be called on post-operative day one by a study investigator. In addition to the routine post-operative day one phone call to the patient, all participants will receive instructions and a business card in order to have a point of contact to report a potential adverse event at any time during or after the study period. They will also be specifically informed that they should receive emergency department care for any signs and symptoms of hypotension. Patients who will not have anyone present at home after discharge will receive a same-day follow-up phone call from the study team to screen for adverse events.

The study remains blinded during the second year of enrollment and no interim analysis of efficacy has been performed. No adverse events have been reported by any study participants.

All adverse events will be recorded by the research team in a non-anonymized fashion and reported directly to the Mount Sinai Institutional Review Board.

The study team will report the following to the Institutional Review Board and FDA within 5 business days of when they became aware of the event:

Any event that, in the principal investigator's opinion, is unexpected and at least probably related to the study.

Any event that is expected but occurring with greater frequency/intensity will be reported to the Institutional Review Board and FDA within 5 business days.

	Protocol Title:	Olanzapine for the treatment of Post-Discharge Nausea and Vomiting after Ambulatory Surgery
	Principal Investigator Name/Contact Info:	[name] [contact]
	Primary Contact Name/Contact Info:	[name] [contact] [name] [contact]
	Date Revised:	1/31/2018
	Study Number:	GCO#15-1297; HSM# 15-00501

The study team will report the following to the IRB and FDA on an annual basis:

All expected adverse events

The principal investigator will not enroll any new patients until the IRB has reviewed and responded to the report. The study team will continue to follow patients who are already enrolled.

Enrollment will continue once the IRB approves.

j) Withdrawal of Subjects

Patients may be withdrawn from the study without their consent if their eligibility changes from the time of initial consent to the start of surgery or, if in the opinion of the investigator, they are not appropriate for olanzapine administration.

6) Risks to Subjects

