Specifically, a trial comparing olanzapine versus aprepitant for prevention of CINV found no difference in scores between groups in a multi-symptom patient-reported outcome measure (MD Anderson Symptom Inventory (MDASI)), including drowsiness and fatigue.¹³ A trial examining the effectiveness of olanzapine for treatment of breakthrough CINV similarly found no difference between groups in MDASI scores.¹⁴ Another study comparing olanzapine with 5-hydroxytryptamine 3 (5-HT₃) receptor antagonists for prevention of CINV found significant improvements in global health status, emotional functioning, social functioning, fatigue, nausea and vomiting, insomnia and appetite in the olanzapine group. There were no differences in weight, blood lipid or blood glucose levels between groups.¹⁵ These trials support the safety and tolerability of short-term use of olanzapine.

Unlike the cancer patients receiving olanzapine for the prevention or treatment of CINV, patients in this study will be receiving general anesthesia and several other central nervous system depressing (CNS) medications, including intraoperative midazolam and fentanyl, and postoperative oxycodone. The combination of olanzapine and these medications may increase the risk of adverse events not seen in the patients studied for CINV. These risks include sedation, respiratory depression, extrapyramidal symptoms, orthostatic hypotension and cardiac rhythm abnormalities

7) Provisions for Research Related Injury

Subjects will be monitored during surgery and during recovery from anesthesia. Upon discharge, subjects will be provided with a phone number to call should they have any concerns related to surgery, anesthesia, or the study. If necessary, subjects will be instructed to return to the hospital should any complication requiring medical attention occur.

	Protocol Title:	Olanzapine for the treatment of Post-Discharge Nausea and Vomiting after Ambulatory Surgery
	Principal Investigator Name/Contact Info:	[name] [contact]
	Primary Contact Name/Contact Info:	[name] [contact] [name] [contact]
	Date Revised:	1/31/2018
	Study Number:	GCO#15-1297; HSM# 15-00501

Subjects who are injured as a result of this study will be treated until the resolution of the adverse event and the cost billed to them and/or their insurance carrier. Patients will not be compensated for research related injury.

8) Potential Benefits to Subjects

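### The five combination risks the protocol names and the pre-discharge orthostatic result have no field in the listed data, and the 5-business-day reporting triggers have no seriousness term

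*Combined protocol and SAP*

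**What the plan says.** **Risks.** Section 6 (Risks to Subjects) notes that, unlike chemotherapy patients, these subjects also receive general anaesthesia, midazolam, fentanyl and oxycodone, and that the combination may bring harms not seen in the chemotherapy studies: "These risks include sedation, respiratory depression, extrapyramidal symptoms, orthostatic hypotension and cardiac rhythm abnormalities".

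**Data.** Section 5(f) says the relevant data come from the anaesthesia record, the electronic record and the telephone interviews, "collected on standardized forms by trained study personnel", and then lists the items. Nausea and vomiting in the PACU "will be assessed at 30, 60, and 120 minutes after surgery by trained study personnel". Before PACU discharge, "subjects will be assessed for signs of orthostatic hypotension". Of the day-one telephone interview the section says: "At this time investigators will also screen for adverse events".

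**Safety text before section 5(j).** Patients with nobody at home get a same-day call to screen for adverse events, and every participant gets a contact for reporting events at any time. All adverse events are recorded and sent to the IRB. On experience to date, in the second year of enrolment: "No adverse events have been reported by any study participants".

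**Reporting.** Two kinds of event go to the IRB and FDA within 5 business days: those unexpected and at least probably related in the principal investigator's opinion, and those expected but more frequent or more intense. Expected events go to both bodies annually. A further sentence pauses enrolment until the IRB has responded to the report.

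**The concern.** By the protocol's own account, the chemotherapy record does not settle the safety of this combination. The trial is randomized and blinded, so it could give an unbiased by-arm comparison of the named harms to set beside any antiemetic benefit. The one earlier perioperative study cited in section 2, which the protocol calls small, did compare named adverse events between groups. If the same question is not put to every patient and the answer recorded, the comparison here will be weaker than the design allows.

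The reporting rules raise a separate matter. They sort events by expectedness, relatedness, frequency and intensity, but not by seriousness. Section 6 lists serious outcomes, including death, as known risks of chronic use, so the word 'expected' can carry more weight than its authors probably meant.

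**Working it through.** **Step 1. Set the named risks against the data list.** The list runs from age to post-discharge nausea and has 21 items: baseline factors, drug totals, surgery duration, PACU stay, rescue antiemetics, nausea and vomiting.

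| Risk named in section 6 | Field among the 21 | Named in section 6's chronic-use list |
|---|---|---|
| Sedation | none | yes (somnolence) |
| Respiratory depression | none | no |
| Extrapyramidal symptoms | none | yes |
| Orthostatic hypotension | none, although checked in every subject | yes (postural hypotension) |
| Cardiac rhythm abnormalities | none; the ECG is a pre-operative eligibility check | no |

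Result: 0 of 21 items covers any of the five risks, and 2 of the 5 are not named in the chronic-use list.

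**Step 2. What a general screen leaves behind.** For each harm a patient may have reported it, been asked and denied it, or not been asked about it. An adverse-event record captures the first. Nothing in the listed data separates the second from the third, so a harm has a numerator but no documented number assessed.

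With a recorded answer for every patient, zero events in n patients gives an exact two-sided 95% upper limit of U = 1 − 0.025^(1/n):

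- n = 70 (half of 140, assuming 1:1 allocation, which is not stated): 5.1%
- n = 60: 6.0%
- n = 40: 8.8%

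These limits reflect the number of patients and do not measure the fault. They show what a known denominator allows one to say.

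**Step 3. How many patients a change could still reach.** Section 5(d) expects 20 to 30 completers a year, and the safety text places the trial in its second year. Completed so far: 20 (start of year two at 20 a year) to 60 (end of year two at 30 a year). Remaining: 140 − 60 = 80 to 140 − 20 = 120, that is 57% to 86%, or 40 to 60 per arm if 1:1.

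**Step 4. Run cases through the reporting rules.**

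- Unexpected and at least probably related, of any severity: 5 business days, IRB and FDA.
- Expected but more frequent or intense: 5 business days, IRB and FDA.
- Serious, of a type in the chronic-use list (16 entries under the rare-but-serious heading), read as expected and not judged more frequent or intense: annual report.
- Serious, unexpected, judged only possibly related: neither trigger. It falls under the general sentence on reporting to the IRB, which gives no deadline and does not mention the FDA.
- Respiratory depression or a rhythm abnormality: the route depends on whether the reference for 'expected' is the chronic-use list or the combination-risk paragraph, which the text does not say.

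The enrolment-pause sentence follows the annual list and does not say which report it means.

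**The case against.** The strongest reply is that the plan does ask. It has the day-one screen, the same-day call for patients alone at home, a contact for reporting at any time, a study physician always available (section 4), and recording of all events. A subject who meets the orthostatic criteria is evaluated and treated, so positives should appear in the chart. Section 5(f) also draws postoperative data from the electronic record. All of this stands. A reader might infer from the statement that no events have been reported that nobody was asked; the documents do not support that. What remains is that the asking is not visibly uniform and that negatives are not visibly recorded.

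A reader might also make a timing argument: the dose is taken "within one hour prior to entering the operating room", section 2 puts peak concentration at about 6 hours, and the last fixed PACU assessment is at 120 minutes. This does not size the problem. The day-one call can cover the whole interval, the orthostatic check is tied to discharge and not to 120 minutes, and time in the operating room is not given.

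On reporting, the first trigger is broad because it has no seriousness threshold, and all events reach the IRB. A rare listed event could also meet the frequency trigger: the list puts these types below 1%, and one case in 70 olanzapine patients is 1/70 = 1.4%. But one in 140 is 0.7%, the listed rates come from chronic use, and the text names neither a reference rate nor a denominator. That route is arguable, not assured. It is also fair that where to set the relatedness threshold is a choice; the documents contain no standard that makes 'probably' wrong.

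Finally, the body of section 5(h), the start of the safety section, the standardized forms and appendix 1 were not visible. A call script or adverse-event form may be there. This limits the point but does not remove it, because the data list itself is complete.

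**Conclusion.** The point holds as a worthwhile, low-cost improvement, with medium confidence. In the visible text, none of the 21 data items covers the five risks the protocol itself names, and a check planned for every subject has no listed result. The fault is unstructured asking, not absence of asking. Its effect on the by-arm comparison cannot be put as a number, since the documents give no basis for the share of events a general screen would miss.

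On reporting, the rules as written can leave a serious event of a listed type to the annual FDA report, and they give no FDA route or deadline for an unexpected serious event judged only possibly related. A reader might infer that such events would go unreported altogether; they would not, because all adverse events go to the IRB.

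The 80 to 120 patients still to come rest on the stated pace having held, and the per-arm figures on 1:1 allocation.

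**What to change.** **Data.**

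- Add the orthostatic result to the section 5(f) list as yes/no/not assessed, with the values.
- At the existing day-one call, read a fixed yes/no checklist of the named symptoms in the same words to every patient.
- Take sedation, respiratory and rhythm events, with written definitions, from the records already reviewed.
- Tabulate each item by arm with its denominator and a 95% CI, showing patients before and after the change separately.

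**Reporting.**

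- Add a seriousness criterion to the 5-business-day list that also settles the route for serious events judged only possibly related.
- State that appearing in the section 6 list does not by itself make a serious event reportable only annually.
- Name the reference list for 'expected' and say where respiratory depression and cardiac rhythm abnormalities stand.
- Reconcile these rules with the general IRB sentence, and say which report the enrolment-pause sentence means.

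**Cost.** A few form fields, a wider record review, one table and a short rewrite; no new visit or procedure. Safety data will be incomplete for the roughly 20 to 60 patients already treated unless records allow recovery, counts before and after the change cannot simply be pooled, and there will be somewhat more expedited reports. If the forms, appendix 1 or the unseen safety text already cover any of this, a cross-reference is enough.
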